7.1.1.5 Centralized Review of Radiology

Radiographic assessments will be performed by a Radiologist at UCSF without knowledge of patients' clinical responses to protocol therapy for all patients' imaging studies during the first 6 months' on therapy (including imaging after completion of cycle 6). For patients enrolled on study at the Robert H. Lurie Comprehensive Cancer Center of Northwestern University, standard CT or MRI images will be acquired at that study site, stored on a CD as DICOM images, and shipped via FEDEX to the designated UCSF study coordinator. After cycle 6 imaging, RECIST 1.1 measurements may be performed at the treating site by a qualified investigator or radiologist. See Study Laboratory and Procedures Manual for detailed instructions.

Initial assessment of response or progression may be made based upon standard of care Radiology review plus clinical assessment if RECIST 1.1 measurements are not available at the time of study visit. In patients without signs of clinical progression, progression must be confirmed by RECIST 1.1 prior to removal from study. If progression is identified by RECIST 1.1 that was not identified by standard of care Radiology review plus clinical assessment, a patient will be removed from study at date of next scheduled study visit. Efforts will be made to obtain RECIST 1.1 measurements for patients treated at both sites within approximately 7 days of start of odd cycles.

7.1.2 Time to Event Endpoints

Time to Progression (TTP)

TTP is defined as the duration from date of first dose of protocol therapy to date of removal from study for radiographic (per RECIST 1.1) and/or clinical progression including death attributed to progression. For patients removed from study for other reasons than progression (such as toxicity, withdrawal of consent, death without documented progression, or other reasons without clinical or radiographic evidence of tumor progression), TTP will be censored at the date of study discontinuation.

Time to Treatment Failure (TTF)

TTF will be measured from date of first dose of protocol therapy to date of study discontinuation for progression, death, or toxicity. For patients removed from study for other reasons (such as noncompliance or withdrawal of consent), TTF will be censored at the date of study discontinuation.

Progression-Free Survival

Progression-free survival (PFS) is defined as the duration of time from date of first dose of protocol therapy to time of documented radiographic and/or clinical disease progression or death from any cause. Patients who have not progressed or died are censored at the date last known to be progression-free.

Overall Survival (OS)

Median OS for all enrolled patients who receive at least one dose of protocol therapy will be calculated from date of first dose of protocol therapy until date of death, using chart review and/or follow up phone calls to determine date of death in patients after removal from study. The survival of patients still alive after 5 years of follow up post study discontinuation will be censored. Alive patients are censored at the date last known alive.

7.2 Evaluation of Safety

Analyses will be performed for all patients having received at least one dose of study drug. The study will use the [CTCAE Version 4.0](#) for reporting of non-hematologic adverse events and hematologic adverse events.

7.3 Evaluation of Exploratory Endpoints

Assessment of CTC enumeration, and patient blood specimen banking) is described below. Other exploratory endpoints (specifically, indices of viral hepatitis reactivation, and correlation between outcome measures and cause of viral hepatitis) will be measured/performed according to standard institutional procedures.

7.3.1 Circulating Tumor Cell Measurements

CTC will be enumerated using a novel slide-based assay (CEpiC) at baseline and on Day 1 of Cycles 2 and 3 (up to 7 days before treatment date). The slide-based circulating epithelial cell assay (CEpiC) is a new methodology to identify circulating epithelial cells and credential them as tumor cells. In the assay, each tube of approximately 7.5 mL (0.5 TBS) of anti-coagulated peripheral blood is lysed and all mononuclear cells are plated on cell adhesion glass slides. After appropriate pre-processing, the monolayer is incubated with a pan-anti-cytokeratin antibody and subsequently with a secondary fluorescent antibody. The samples are also stained with the nuclear stain DAPI. Slides are then analyzed with an automated digital microscope and data analyzed and correlated. The analysis predominantly consists of a cytometric and morphologic correlation that identifies intact cells that have a cytoplasmic cytokeratin stain consistent with epithelial cells. Controls include identically processed normal donor blood and sub-sampling of the patient blood excluding the primary antibody. The result of the CEpiC assay is the count of positive CEpiCs per milliliter of peripheral blood with associated imagery. CTC testing and analysis will be performed in the laboratory of [name]., at the Scripps Research Institute, with the assistance of the clinical coordinator, [name]. CTC testing will be performed without knowledge of the patients' clinical status.

Please see Study Laboratory and Procedures Manual for instructions regarding the collection, shipping, and handling of blood specimens for the CEpiC assay.

7.3.2 Markers of mTOR Pathway Activation

Archival tumor blocks will be accessioned then sectioned into 5 µm slides (3-5 plus H&E) and submitted to the UCSF Immunohistochemistry Core to perform IHC for selected mTOR pathway activation markers such as pAKT (S473), pS6RP (S235/236), PTEN (rabbit polyclonal antibody PN37), and LKB1 (D60C5). Optimization for each antibody will be performed using breast tumor samples as positive controls. The Director of the Core, [REDACTED], will read and provide reports for each case including intensity (0-3+), percentage positivity, distribution (very focal, focal, diffuse), and intracellular localization (membranous, cytoplasmic, nuclear) for each stain.⁷⁻¹⁰

In addition, FFPE sections from consenting patients will be submitted to the UCSF Clinical Cancer Genomics Lab (CCGL) for sequencing using hybridization-based target enrichment to analyze ~539 cancer-related genes for mutations (including mTOR pathway genes such as mTOR, AKT, TSC1/2, PTEN, PIK3CA) and copy number changes; selected genes will be analyzed for structural rearrangements (<http://cancer.ucsf.edu/CCGL>). Paired whole blood samples also will be sequenced for germline comparison.

7.3.3 Blood Specimen Banking

Blood samples totaling approximately 15-20 mL (1 to 1.3 TBS) optional patient blood samples (including serum, PBMC, whole blood, and plasma) will be obtained from all patients enrolled on this study additional potential future biomarker research. These blood samples will be taken at baseline, before temsirolimus dose on Cycle 1 Day 8, after completing 2 cycles of therapy (8 weeks ± 7 days), and at the end of treatment (if ≥ 4 weeks since last specimen(s) banked). For sample processing, handling, and shipping see Study Laboratory and Procedures Manual. The analyses will be performed by an investigator-approved laboratory.

7.3.4 Tumor Specimen Banking

Fresh specimen or formalin-fixed paraffin-embedded diagnosis tumor tissue and/or 10 to 20 unstained slides plus H&E slide from a tumor tissue block as well as corresponding pathology reports from initial diagnosis and/or subsequent tumor sampling will be retrospectively obtained. Specimens will be requisitioned from Pathology Department for banking as soon as possible after start of study. See Specimen Banking Procedures Manual.

8. Reporting and Documentation of Adverse Events

8.1 Definitions of Adverse Events

8.1.1 Adverse Event

An adverse event (also known as an adverse experience) is defined as any untoward medical occurrence associated with the use of a drug in humans, whether or not considered drug related. More specifically, an adverse event (can be any unfavorable and unintended sign (e.g., an abnormal laboratory finding), symptom, or disease temporally associated with the use of a drug, without any judgment about causality. An adverse event can arise from any use of the drug (e.g., off-label use, use in combination with another drug) and from any route of administration, formulation, or dose, including an overdose.

8.1.2 Adverse reaction

An adverse reaction is defined as any adverse event caused by the use of a drug. Adverse reactions are a subset of all suspected adverse reactions for which there is reason to conclude that the drug caused the event.

8.1.2.1 Suspected

A suspected adverse reaction is defined as any adverse event for which there is a reasonable possibility that the drug caused the adverse event. For the purposes of IND safety reporting, "reasonable possibility" indicates that there is evidence to suggest a causal relationship between the drug and the adverse event. A suspected adverse reaction implies a lesser degree of certainty about causality than an adverse reaction.

8.1.2.2 Unexpected

An adverse event or suspected adverse reaction is considered *unexpected* if it is not listed in the investigator brochure or package insert(s), or is not listed at the specificity or severity that has been observed, or, if an investigator brochure is not required or available, is not consistent with the risk information described in the general investigational plan or elsewhere in the current application.

"Unexpected," as used in this definition, also refers to adverse events or suspected adverse reactions that are mentioned in the investigator brochure as occurring with a class of drugs or as anticipated from the pharmacological properties of the drug, but are not specifically mentioned as occurring with the particular drug under investigation.

Adverse events that would be anticipated to occur as part of the disease process are considered *unexpected* for the purposes of reporting because they would not be listed in the investigator brochure. For example, a certain number of non-acute deaths in a cancer trial would be anticipated as an outcome of the underlying disease, but such deaths would generally not be listed as a suspected adverse reaction in the investigator brochure.

Some adverse events are listed in the Investigator Brochure as occurring with the same class of drugs, or as anticipated from the pharmacological properties of the drug, even though they have not been observed with the drug under investigation. Such events would be considered *unexpected* until they have been observed with the drug under investigation. For example, although angioedema is anticipated to occur in some patients exposed to drugs in the ACE inhibitor class and angioedema would be described in the investigator brochure as a class effect, the first case of angioedema observed with the drug under investigation should be considered *unexpected* for reporting purposes.

8.1.2.3 Serious

An adverse event or suspected adverse reaction is considered *serious* if, in the view of either the investigator or sponsor, without regard to causality, it results in any of the following outcomes:

- Death
- Life-threatening adverse event
- Inpatient hospitalization or prolongation of existing hospitalization
- A persistent or significant disability or incapacity
- Congenital anomaly/birth defect
- Results in cancer

Important medical events that may not result in death, are life-threatening, or require hospitalization may be considered serious when, based upon appropriate medical judgment, they may jeopardize the patient or subject and may require medical or surgical intervention to prevent one of the outcomes listed in this definition. Examples of such medical events include allergic bronchospasm requiring intensive treatment in an emergency room or at home, blood dyscrasias or convulsions that do not result in inpatient hospitalization, or the development of drug dependency or drug abuse.

8.1.2.4 Life-threatening

An adverse event or suspected adverse reaction is considered *life-threatening* if, in the view of the sponsor-investigator, its occurrence places the patient or subject at immediate risk of death. It does not include an adverse event or suspected adverse reaction that, had it occurred in a more severe form, might have caused death.

8.2 Recording of an Adverse Event

All grade 3 and above adverse events will be entered into OnCore[®], whether or not the event is believed to be associated with use of the study drug. Data about these events and their severity will be recorded using the NCI CTCAE v4.0.

The Investigator will assign attribution of the possible association of the event with use of the investigational drug, and this information will be entered into OnCore[®] using the classification system listed below:

Relationship	Attribution	Description
Unrelated to investigational drug/intervention	Unrelated	The AE is clearly NOT related to the intervention
	Unlikely	The AE is doubtfully related to the intervention
Related to investigational drug/intervention	Possible	The AE may be related to the intervention
	Probable	The AE is likely related to the intervention
	Definite	The AE is clearly related to the intervention

Signs or symptoms reported as adverse events will be graded and recorded by the Investigator according to the CTCAE. When specific adverse events are not listed in the CTCAE they will be graded by the Investigator as *none, mild, moderate* or *severe* according to the following grades and definitions:

- Grade 0 No AE (or within normal limits)
- Grade 1 Mild; asymptomatic or mild symptoms; clinical or diagnostic observations only; intervention not indicated
- Grade 2 Moderate; minimal, local, or noninvasive intervention (e.g., packing, cautery) indicated; limiting age-appropriate instrumental activities of daily living (ADL)
- Grade 3: Severe or medically significant but not immediately life-threatening; hospitalization or prolongation of hospitalization indicated; disabling; limiting self-care ADL
- Grade 4: Life-threatening consequences; urgent intervention indicated
- Grade 5: Death related to AE

8.3 Follow-up of Adverse Events

All adverse events will be followed with appropriate medical management until resolved. Patients removed from study for unacceptable adverse events will be followed until resolution or stabilization of the adverse event. For selected adverse events for which administration of the investigational drug was stopped, a re-challenge of the subject with the investigational drug may be conducted if considered both safe and ethical by the Investigator.

8.4 Adverse Events Monitoring

All adverse events, whether or not unexpected, and whether or not considered to be associated with the use of the study drug, will be entered into OnCore[®], as noted above.

The Investigator will assess all adverse events and determine reportability requirements to the UCSF Data and Safety Monitoring Committee (DSMC) and UCSF’s Institutional Review Board, the Committee on Human Research (CHR); and, when the study is conducted under an Investigational New Drug Application (IND), to the Food and Drug Administration (FDA) if it meets the FDA reporting criteria.

All adverse events entered into OnCore[®] will be reviewed by the Helen Diller Family Comprehensive Cancer Center Site Committee on a weekly basis. The Site Committee will review and discuss at each weekly meeting the selected toxicity, the toxicity grade, and the attribution of relationship of the adverse event to the administration of the study drug(s).

In addition, all adverse events and suspected adverse reactions considered “serious,” entered into OnCore[®] will be reviewed and monitored by the Data and Safety Monitoring Committee on an ongoing basis, discussed at DSMC meetings which take place every six (6) weeks.

8.5 Expedited Reporting

Reporting to the Data and Safety Monitoring Committee

If a death occurs during the treatment phase of the study or within 30 days after the last administration of the study drug(s) and it is determined to be related either to the study drug(s) or to a study procedure, the Investigator or his/her designee must notify the DSMC Chair (or qualified alternate) within 1 business day of knowledge of the event. The contact may be by phone or e-mail.

Reporting to UCSF Committee on Human Research (Institutional Review Board)

The Principal Investigator must report events meeting the UCSF CHR definition of "Unanticipated Problem" (UP) within 5 business days of his/her awareness of the event.

Expedited Reporting to the Food and Drug Administration

If the study is being conducted under an IND, the Sponsor-Investigator is responsible for determining whether or not the suspected adverse reaction meets the criteria for expedited reporting in accordance with Federal Regulations (21 CFR §312.32).

The Investigator must report in an IND safety report any suspected adverse reaction that is both serious and unexpected. The Sponsor-Investigator needs to ensure that the event meets all three definitions:

- Suspected adverse reaction (as defined in 8.1.2.1)
- Unexpected (as defined in 8.1.2.2)
- Serious (as defined in 8.1.2.3)

If the adverse event does not meet all three of the definitions, it should not be submitted as an expedited IND safety report.

The timeline for submitting an IND safety report to FDA is no later than **15 calendar days** after the Investigator determines that the suspected adverse reaction qualifies for reporting (21 CFR 312.32(c)(1)).

Any unexpected fatal or life-threatening suspected adverse reaction will be reported to FDA no later than **7 calendar days** after the Investigator's initial receipt of the information (21 CFR 312.32(c)(2)).

Any relevant additional information that pertains to a previously submitted IND safety report will be submitted to FDA as a Follow-up IND Safety Report without delay, as soon as the information is available (21 CFR 312.32(d)(2)).

8.6 Adverse Event Reporting to Funding Organization and Research Grant Provider

In addition to complying with all applicable regulatory reporting laws and regulations, each site will report the following information in writing to NCCN and research grant provider (Pfizer) in writing within 24 hours of the Investigator's awareness of occurrence. Principal Investigator should report SAEs as soon as they are determined to meet the definition, even if complete information is not yet available:

- a) a death, regardless of whether it is considered related to treatment with the Study Drug

- b) a non-fatal SAE that occurs during the reporting period and that is assessed by the Principal Investigator as both related to treatment with the Study Drug and unexpected for that product
- c) an SAE assessed by the Principal Investigator as related to the Study Drug that occurs after the SAE reporting period,
- d) an otherwise reportable event - Exposure During Pregnancy, Exposure During Lactation, Occupational Exposure, and Lack Of Effect. Even though there may not be an associated SAE, exposure to the Study Drug during pregnancy, exposure to the Study Drug during lactation, and occupational exposure to the Study Drug are reportable, and lack of effect of the Study Drug may also be reportable.

An event should be considered “related” to the Study Drug if a relationship is at least a reasonable possibility, and “unexpectedness” should be based upon a single safety reference document identified by the Principal Investigator and documented in association with the study.

Follow-up information regarding any of the above

- The participating investigator should include his or her assessment of the causal relationship between each SAE and the research grant provider’s product.
- Reports to NCCN will include the cover page provided (see Appendix J attached hereto), and reference Protocol Number NCCN-T12. Submit to NCCN via fax at [name] or via e-mail to [contact]
- Reports to Pfizer, Inc. will include the Reportable Event Fax Cover sheet (see Appendix 3.1) (use NCCN-T12 as the external reference number). Submit to the Pfizer U.S. Clinical Trial Department [REDACTED].
- A copy of the report should be sent to the coordinating center CRC

9. Statistical Considerations and Evaluation of Results

9.1 Study Endpoints

9.1.1 Study Design

This study is a single-arm, one-stage, open-label phase II trial to evaluate the efficacy of the combination of temsirolimus plus sorafenib in first line therapy for patients with histologically-confirmed advanced HCC.

9.1.2 Primary Endpoint

Median TTP will be calculated in months from date of first dose of protocol therapy to date of removal from study for radiographic (per RECIST 1.1) and/or clinical progression including death attributed to progression. For patients removed from study for other reasons than progression (such as toxicity, withdrawal of consent, or death from other causes than documented radiographic and/or clinical progression), TTP will be censored at the date last known to be progression-free.

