Duration of study	The study will reach completion approximately 24 months from the time the study opens to accrual. The study will end 5 years after the final patient discontinues treatment or after all patients are deceased, whichever comes first.

Abstract

Study Drugs
	
Temsirolimus: 10 mg weekly will be administered intravenously over 30 to 60 minutes using an infusion pump starting on Cycle 1, Day 1 of study enrollment.
 
Sorafenib: 200 mg tablet twice daily starting on Cycle 1, Day 1 of study enrollment after completion of temsirolimus infusion.

Safety Assessments
	
Analyses will be performed for all patients having received at least one dose of study drug. The study will use the NCI (CTCAE) Version 4.0.

Efficacy Assessments
	
Primary Endpoint Median TTP will be calculated in months from date of first dose of protocol therapy to date of removal from study for progression; Kaplan-Meier methods will be used to summarize the primary endpoint (median TTP).
 
Secondary Endpoints Response rate (RR) will be measured by RECIST version 1.1; measurements will be presented descriptively for the study cohort.
 
Median PFS will be calculated in months from date of first dose of protocol therapy to date of documented disease progression or death from any cause. Kaplan-Meier methods will be used to summarize time-to-event outcomes including the primary endpoint (median TTP) and secondary endpoints (PFS, TTF, OS).
 
Median OS for all enrolled patients who receive at least one dose of protocol therapy will be calculated from date of first dose of protocol therapy until date of death, using chart review and/or follow up phone calls to determine date of death in patients after removal from study.
 
TTF will be measured from date of first dose of protocol therapy to date of study discontinuation for progression, death, or toxicity.
 
In patients with baseline AFP ≥ 20 ng/mL, AFP response will be measured by the percent change from baseline value to the value at the time of best AFP response. The change in AFP will also be examined for association with absolute TTP and best response.

Abstract

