2.4 Endpoints

2.4.1 Primary Endpoint

- Median TTP will be calculated in months from date of first dose of protocol therapy to date of removal from study for progression. For patients removed from study for other reasons than progression (such as toxicity, withdrawal of consent, death without documented progression, or other reasons without clinical or radiographic evidence of tumor progression), TTP will be censored at the date last known to be progression-free.

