7.1 Evaluation of Efficacy (or Activity)

7.1.1 Measurement of Response and Progression

Target and non-target lesions will be defined by RECIST guidelines (version 1.1): (Therasse, Arbuck et al. 2000) (Eisenhauer, Therasse et al.) All enrolled patients will imaging of chest, abdomen, and pelvis at baseline and after every 2 cycles (8 weeks \pm 7 days) of protocol therapy. RECIST 1.1 measurements will be performed by centralized radiologist at UCSF, without knowledge of patients' clinical responses to protocol therapy, imaging studies during first 6 months on protocol therapy (including post-cycle 6 imaging), then at each study site by qualified investigator and/or radiologist for subsequent studies for patients who remain on protocol therapy. The schedule and methods of radiographic evaluation are described in previous sections.

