The duration of overall response is measured from the time measurement criteria are met for CR or PR (whichever is first recorded) until the first date that recurrent or progressive disease is objectively documented (taking as reference for progressive disease the smallest measurements recorded since the treatment started).

The duration of overall CR is measured from the time measurement criteria are first met for CR until the first date that recurrent disease is objectively documented.

Duration of stable disease

Stable disease is measured from the start of the treatment until the criteria for progression are met, taking as reference the smallest measurements recorded since the treatment started.

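### TTP is dated at removal from study, which can only push scan-detected progression later, and the sections disagree on its censoring date and on deaths attributed to progression

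*Combined protocol and SAP*

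**What the plan says.** **Event date.** The Abstract and 2.4.1 run TTP from first dose "to date of removal from study for progression". Sections 7.1.2 and 9.1.2 end it at the "date of removal from study for radiographic (per RECIST 1.1) and/or clinical progression including death attributed to progression". All four places agree on removal.

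**When removal happens.** Under 6.1.2.2 and 7.1.1.5, a patient without clinical progression needs RECIST 1.1 confirmation before removal. Progression seen by RECIST but missed by routine review leads to removal at the next scheduled visit. Scans through cycle 6 are read centrally at UCSF, and the second site ships its images there. RECIST measurements are aimed for within about 7 days of the start of odd cycles. Section 6.1.4 defines End-of-Treatment as the day of the decision to discontinue.

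**Censoring.** Section 2.4.1 states that "TTP will be censored at the date last known to be progression-free", and 9.1.2 agrees. Section 7.1.2 states that "TTP will be censored at the date of study discontinuation".

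**Deaths.** Sections 7.1.2 and 9.1.2 count death attributed to progression as an event. Sections 2.4.1 and 7.1.2 list among the reasons for censoring "death without documented progression, or other reasons without clinical or radiographic evidence of tumor progression". The 9.1.2 censoring clause covers deaths from causes other than *documented* radiographic or clinical progression.

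**PFS.** The Abstract, 2.4.2 and 7.1.2 end PFS at documented progression or death. Section 9.1.3 ends it at study removal for progression, or death.

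**Use of the result.** Section 1.3 says a randomized trial is indicated if median TTP reaches at least 6 months; 9.2.1 says one should be considered. Section 9.4.2 reports the Kaplan-Meier median and the proportion with TTP of 6 months or more.

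**The concern.** Removal is an administrative date that can come after the disease event. In a randomized trial such a lag might largely cancel between arms. Here nothing cancels it, because 9.2.1 compares the result with a 3-month historical null and a 6-month target. The week-24 scan falls shortly before 6 months, so a patient who progresses on it can be credited with 6 months by the timing of removal.

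The protocol dates progression by the disease elsewhere. In 7.1.1.4, "Stable disease is measured from the start of the treatment until the criteria for progression are met", and response lasts "until the first date that recurrent or progressive disease is objectively documented". Under 2.4.2 and 7.1.2 a patient's TTP can even be later than the PFS for the same progression.

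The conflicts on censoring and deaths do not depend on any lag. Two analysts who each follow the protocol could report different primary results, and with 25 patients one reclassified event is visible.

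**Working it through.** **1. Reproduce the design.** From 9.2.1: n = 25, one-sided alpha 10%, 6-month rates 25% versus 50%, exponential TTP. The rates match the medians: 0.5^(6/3) = 0.25 and 0.5^(6/6) = 0.50. No cut-off is stated. P(X ≥ 9 | 25, 0.25) = 14.9% exceeds 10%, and P(X ≥ 10 | 25, 0.25) = 7.1% does not, so the implied rule is 10 of 25. Its power is P(X ≥ 10 | 25, 0.50) = 88.5%, against the stated 88%.

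**2. Place the scans against 6 months.** With 1 month = 30.44 days, 6 months = 182.6 days. The week-24 scan is nominally on day 168, with a window of ±7 days (6.1.2.2). The gap is 182.6 − 168 = 14.6 days, or 182.6 − 175 = 7.6 days at the end of the window.

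**3. See which lags can matter.** A scan at most 7 days late plus a lag of at most 7 days gives 14 days, short of 14.6. So lags up to 7 days cannot carry a week-24 progression past 6 months. If the scan offset is uniform on ±7 days and the lag uniform on 0-14 days, the chance that their sum exceeds 14.6 is (21 − 14.6)² / (2 × 14 × 14) = 0.104. At a 3-month median, 42.7% − 27.9% = 14.8% of patients have progression first seen at week 24. Hence about 0.104 × 14.8 = 1.5 percentage points move from failure to success.

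**4. Type I error of the 10-of-25 rule.** Simulation with a true median of 3 months, 8-week scans within ±7 days, and early leavers counted as failures. Lags and dropout are assumptions.

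| Dropout by 6 months | No lag | 0-7 days, all | 0-14 days, half | 0-14 days, all |
|---|---|---|---|---|
| 0% | 13.3% | 13.3% | 15.4% | 17.8% |
| 10% | 7.4% | 7.4% | 8.8% | 10.3% |
| 20% | 3.6% | 3.6% | 4.4% | 5.2% |

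The 13.3% at zero lag comes from the scan grid, not from removal dating: with scans exactly on schedule the success rate is 0.5^(168/91.3) = 0.279, and P(X ≥ 10 | 25, 0.279) = 13.2%.

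**5. Kaplan-Meier median of 6 months or more** (10% dropout). For a true median of 5.5 months the probability is 49.3% with the documented date, and 51.9% or 54.3% with lags of 0-14 days in half or all patients. For a true median of 3 months it is 1.2%, 1.5% and 1.8%.

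**6. Censoring date.** True median 5.5 months. If the date last known progression-free means the last scan, the mean 6-month Kaplan-Meier value is 0.4935 instead of 0.4992 (10% dropout), or 0.4870 instead of 0.4992 (20%). That is about 0.6 and 1.2 points. It is less if clinic visits count.

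**7. One death.** Suppose 13 of 25 have events before 6 months and nobody else is censored: S(6) = 12/25 = 48.0%. If the j-th of those 13 is censored instead, S(6) = 12/25 × (26 − j)/(25 − j). This gives 50.0% for j = 1, 50.7% for j = 7 and 52.0% for j = 13.

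**The case against.** The removal date is used consistently for TTP. A reader might infer that the sections contradict each other on the event date; they do not. The contrast with 7.1.1.4 is also limited, because duration of response and of stable disease are not listed endpoints. That stands, but a consistent rule can still bias in one direction.

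A reader might also infer a large inflation. Moving every event by a fixed four weeks would give a type I error of 21.9%, and putting half of the week-24 progressions past 6 months would give 38.3%. The documents do not support such lags. The next-visit rule covers only progressions that routine review missed, visits are weekly, and the RECIST target is about 7 days from cycle start. On that nominal path a week-24 progression is read by about day 175 and the patient removed by about day 182, just inside 182.6. A late read, a visit window or a wait for the next cycle could cross the line, but no passage shows that half or all patients would have two-week lags.

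The one-patient example is a knife-edge. It needs exactly 13 events and no other censoring, and it flips only the median criterion, since 12 of 25 already passes the implied 10-of-25 rule. It does not show that one death would decide the trial.

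On deaths, the lists in 2.4.1 and 7.1.2 apply to patients removed for reasons other than progression. A death attributed to progression can be read as outside them, so this is ambiguity more than flat contradiction. Nor is 9.1.2 a clean model to copy: the word *documented* in its censoring clause leaves the same case open.

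**Conclusion.** The point holds at moderate weight. Removal dating can only lengthen TTP for scan-detected progression. Its size rests on lags the documents do not give: essentially nothing up to 7 days, and about 3 to 5 percentage points of type I error (with 10% or no dropout) if every patient had a lag of 0-14 days. On the Kaplan-Meier median the same extreme adds about 5 points at a true median of 5.5 months and under 1 point at 3 months.

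The differences in wording need no assumption. The censoring date in 7.1.2 conflicts with 2.4.1 and 9.1.2, at a cost of about a point. A death attributed to progression but not documented is an event in the first sentence of 9.1.2, can be read as censored in 2.4.1, and meets both wordings in 7.1.2. PFS in 9.1.3 departs from the Abstract, 2.4.2 and 7.1.2. These should be settled before analysis, so that the choice cannot follow the data. The sample-size calculation itself reproduces and is not in question.

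**What to change.** - **Event date.** In the Abstract, 2.4.1, 7.1.2 and 9.1.2, date TTP at the scan first meeting RECIST 1.1 progression or at the recorded date on which the investigator judged clinical progression, whichever is earlier, regardless of removal.
- **Censoring.** Censor all others at the last imaging or documented clinical evaluation at which they were progression-free.
- **Deaths.** State one rule in every section. Death attributed to progression is an event at the date of death if no earlier progression was documented. Death from any other cause without prior progression is censored at the last progression-free assessment. Delete *documented* from the 9.1.2 censoring clause, and delete the death-without-documented-progression example from 2.4.1 and 7.1.2.
- **PFS.** Align 9.1.3 with 2.4.2 and 7.1.2.

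The removal procedures in 6.1.2.2 and 7.1.1.5 need no change. A radiographic-only TTP censored at the last scan can serve as a sensitivity analysis.

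The cost is mostly wording. Scan dates are already collected, but the date of clinical progression must be recorded explicitly, since the protocol gives no criteria for it beyond evaluation of clinical response or deterioration. Observed TTP becomes slightly shorter. If lags really were 0-14 days in everyone, power of the 10-of-25 rule at a 6-month median would fall from about 86% to 83% with 10% dropout. The change does not cure the type I error that comes from the 8-week scan grid.
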